### 6.7.7 Laboratory Evaluations

A summary of observed values and change from baseline will be presented for all laboratory parameters with numerical measures using descriptive statistics. Shift tables displaying low-normal-high at baseline versus low-normal-high at end of study in a 3-by-3 contingency table will be provided. For selected laboratory parameters, scatter plots of baseline versus Week 56 results, will be produced by treatment group.

A laboratory value that is above or below normal range will be considered an abnormal value. For selected laboratory parameters, threshold limits of clinical concern will be defined as multiplicative factors of the normal ranges. The list of multiplicative factors for each laboratory parameter will be included in the Statistical Analysis Plan. The frequency and percentage of subjects with laboratory results above or below the normal range and threshold limits at each scheduled assessment or any time during the treatment will be summarized by treatment group.

**Table 3: Clinical Laboratory Tests**

Fasting blood chemistry	Hematology	Other

 
• albumin
 
• alkaline phosphatase
 
• ALT
 
• AST
 
• GGT
 
• bicarbonate
 
• blood urea nitrogen
 
• serum calcium
 
• serum chloride
 
• serum sodium
 
• creatinine (and estimated creatinine clearance)
 
• glucose
 
• lactate dehydrogenase
 
• serum phosphorus
 
• serum potassium
 
• total and direct bilirubin
 
• total protein
 
• uric acid
 
	
 
• hemoglobin
 
• hematocrit
 
• red blood cell count
 
• red blood cell indices
 
• total white blood cell count
 
• white blood cell differential (neutrophils, lymphocytes, monocytes, eosinophils, and basophils)
 
• platelet count
 
	
 
• thyroid stimulating hormone
 

		Urinalysis
		
 
• midstream urinalysis with reflex microscopic evaluation
 
• pregnancy test (all female subjects)
 

		Urine Drug Screen
		
 
• cannabinoids
 
• amphetamines
 
• cocaine
 
• barbiturates
 
• benzodiazepine
 
• opiates
 

	Lipid panel	
	
 
• total cholesterol
 
• LDL-C
 
• HDL-C
 
• triglycerides
 
	
	Glycemic testing	Serology
	
 
• HbA1c
 
• insulin
 
• glucose
 
	
 
• HBsAg
 
• HCV
 
• HIV
 

All laboratory data will be reported in International System of Units (SI) and Conventional units. Out-of-reference-range values will be flagged as high (H) or low (L) in the listings.

For analysis purposes, values preceded by a "<" or a ">" sign (i.e. those below or above the limits of quantification) will be considered equal to the lower or upper limit of quantification, respectively.

For analysis by visit, analysis windowing as described in Section 5.1 will be utilized for each scheduled visit such that unscheduled visits will also be considered. For each laboratory analyte, the baseline value will be defined as last scheduled or unscheduled value collected prior to the first dose of treatment.

### **6.7.8 Vital Signs**

The following vital signs will be listed and summarized by treatment group and visit.

- Systolic and diastolic blood pressure (mmHg)
- Heart rate (breaths/min)
- Weight (kg)
- respiration rate (breaths/min)
- body temperature (°C or °F)

Vital signs data and changes from baseline in vital signs will be summarized by visit using standard descriptive statistics for the Safety population. The baseline value will be defined as last scheduled or unscheduled value collected prior to the first dose of study treatment. For post-baseline, only data from scheduled visits will be included in the summary tables.

### **6.7.9 Electrocardiograms**

The following quantitative ECG measurements will be listed and summarized by treatment group and visit for the Safety population:

- heart rate (bpm)
- RR interval (msec)
- PR interval (msec)
- QRS interval (msec)
- QT interval (msec)

An overall clinically significant Investigator assessment of ECG will be provided (categories "Yes", "No").

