10.6 Electrocardiograms

Twelve-lead ECG studies will be performed at baseline, and end of study or early termination visits. ECGs will be evaluated for clinically significant abnormalities that would prevent entry into the study, and for arrhythmias, conduction disturbances, or other clinically relevant changes between randomization and each of the subsequent evaluations. Parameters including heart rate, R-R, P-R, QT intervals, and QRS duration will be recorded.

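### The ECG summary uses uncorrected QT only; a per-subject QTcF from the QT and RR already recorded would remove the heart-rate confounding at almost no cost

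*SAP*

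**What the plan says.** Protocol section 10.6 schedules the tracings sparsely: "Twelve-lead ECG studies will be performed at baseline, and end of study or early termination visits". Besides checking eligibility, they are evaluated "for arrhythmias, conduction disturbances, or other clinically relevant changes between randomization and each of the subsequent evaluations". On data capture it says: "Parameters including heart rate, R-R, P-R, QT intervals, and QRS duration will be recorded".

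SAP section 6.7.9 takes over the same five parameters. Its instruction is: "The following quantitative ECG measurements will be listed and summarized by treatment group and visit for the Safety population". The list includes "heart rate (bpm)", "RR interval (msec)" and "QT interval (msec)", together with PR and QRS. The only other ECG output is one overall investigator judgement of clinical significance, recorded as yes or no.

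Neither document mentions a rate-corrected QT, a correction formula, or a QT threshold or change category. Section 6.7.9 also does not mention change from baseline, whereas SAP sections 6.7.7 (laboratory) and 6.7.8 (vital signs) both do.

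**The concern.** Raw QT depends on heart rate even when repolarisation is unchanged. A difference in mean raw QT between arms, or between visits within an arm, therefore mixes a rate effect with any repolarisation effect. If rate rises on active drug, a true lengthening can be offset in the raw QT table. If rate falls, the table can show a lengthening that is only a rate effect.

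Electrocardiograms are a named safety endpoint (Protocol section 6.4, SAP section 3.4). The subjects are aged 12 to 16, and Protocol section 4.0 says that adequate and well-controlled studies of one component, phentermine, have not been done in children. What is at stake is how well one descriptive safety table can be interpreted.

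**Working it through.** The documents state no QT or QTc figure, so there is none to reproduce. The check has three parts.

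**1. Are the data there?** QT and RR are both recorded (Protocol section 10.6) and both summarised (SAP section 6.7.9), so QTc can be derived for each subject without new collection.

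**2. How much does a rate change move raw QT?**

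Formulas: RR (s) = 60/HR and QTcF = QT/RR^(1/3), hence QT = QTcF × (60/HR)^(1/3).

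Assumptions, none from the documents: QTcF constant at 400 ms, baseline 70 bpm, rate changes from −5 to +8 bpm.

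| Change in rate (bpm) | HR | (60/HR)^(1/3) | Raw QT (ms) | Change in raw QT (ms) |
|---|---|---|---|---|
| −5 | 65 | 0.9737 | 389.5 | +9.5 |
| −2 | 68 | 0.9591 | 383.7 | +3.7 |
| −1 | 69 | 0.9545 | 381.8 | +1.8 |
| 0 | 70 | 0.9499 | 380.0 | 0 |
| +1 | 71 | 0.9454 | 378.2 | −1.8 |
| +2 | 72 | 0.9410 | 376.4 | −3.6 |
| +5 | 75 | 0.9283 | 371.3 | −8.6 |
| +8 | 78 | 0.9163 | 366.5 | −13.5 |

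The reverse calculation: if raw QT stays at 380 ms while rate goes from 70 to 75 bpm, QTcF goes from 380/0.9499 = 400.0 to 380/0.9283 = 409.3 ms. A rise of about 9 ms then shows as no change. Over assumed baselines of 70–80 bpm and QT 340–380 ms, an unchanged raw QT corresponds to a QTcF rise of 7.6 to 9.3 ms at +5 bpm, and of 1.6 to 1.9 ms at +1 bpm.

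The correction formula matters too. From 75 bpm and QT 360 ms, a rise of 5 bpm with raw QT unchanged gives +8.4 ms by Fridericia and +13.2 ms by Bazett (square root of RR in place of the cube root).

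**3. Do the planned group means supply QTc?** They do not, because QTc depends on how QT and RR pair within each subject. Take two hypothetical subjects with QT 340 and 380 ms and rates 70 and 80 bpm, paired in the two possible ways:

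- 340 ms at 80 bpm and 380 ms at 70 bpm: QTcF 374.2 and 400.0 ms.
- 340 ms at 70 bpm and 380 ms at 80 bpm: QTcF 357.9 and 418.2 ms.

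Mean QT (360 ms), mean rate (75 bpm) and mean RR are the same in both pairings. Mean QTcF is nearly the same, at 387.1 and 388.1 ms, but the highest value is 400 ms in one and 418 ms in the other. Separate means can roughly indicate an average shift, but they cannot give per-subject values or outlier counts.

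**The case against.** The strongest reply is that nothing is concealed. Heart rate, RR and QT are all listed and summarised, and SAP section 6.7.8 also summarises vital-sign heart rate and its change from baseline by visit. A reader would see a rate shift and could compute QTc from the listings. This stands: what is missing is a pre-specified analysis, and the data for it exist. But deriving QTc later means choosing the formula and cut-offs after the results are known, and the formula changes the answer.

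A reader might infer that phentermine raises heart rate and that the table is therefore biased towards false reassurance. The documents do not support this: they give no heart-rate effect for VI-0521 or its components and raise no QT concern. The confounding argument is general and runs both ways.

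Two further replies also stand. The SAP list matches the protocol list, so the documents do not contradict each other. The protocol's wording is also open-ended, so a machine-read QTc may be captured on the CRF, which is not among these documents; even so, the SAP would not summarise it. And the ECG programme is routine screening: it is scheduled only at baseline and at end of study or early termination, with no replicate tracings or central ECG reading described. QTcF would not make it a reliable test for a shift of a few milliseconds. The investigator's yes/no judgement may catch a marked abnormality in one subject, but is unlikely to show a modest shift between arms.

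**Conclusion.** The point holds as an inexpensive improvement to a descriptive safety analysis. The planned QT summary is confounded by any heart-rate difference between arms, in either direction, and the planned group means do not replace a per-subject correction. Under the stated assumptions (QTcF 400 ms, baseline 70 bpm, Fridericia relation), the distortion is zero with no rate change, about 2 ms for 1 bpm, and about 9 ms for 5 bpm. These figures illustrate the mechanism and do not predict what this trial will show.

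It would go too far to say that the planned outputs cannot answer whether repolarisation changed, because the listings contain what is needed. The primary analysis, the secondary efficacy analyses and the sample size are unaffected.

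**What to change.** In SAP section 6.7.9:

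- Derive QTcF = QT/(RR in seconds)^(1/3) for each subject and ECG. The SAP gives RR in milliseconds, so divide by 1,000 first. Name the formula in the text.
- Summarise QTcF and its change from baseline by arm and visit, alongside the planned raw QT summary, which should stay because it matches Protocol section 10.6.
- If outlier counts are wanted, write the absolute and change categories into the SAP before unblinding.

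The cost is one derived variable and one table, with no new ECGs, readings or data collection. Protocol section 12.1 allows the SAP to add analyses and calls for a protocol amendment only for major changes to the primary endpoint definition or its analysis, so a SAP revision is enough.

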### **6.7.10 Physical Examination**

Abnormalities identified from physical examination are recorded in the eCRF will be listed.

For each physical examination body system, the number and percentage of subjects with abnormalities at baseline and post-baseline will be summarized by treatment group for the Safety population.

## **6.8 Interim Analysis**

No interim analysis is planned.

## 6.9 Data Monitoring Committee

An independent Data Monitoring Committee (DMC) with multidisciplinary representation will be established to evaluate accumulating study data on a periodic basis and to assess the ongoing safety of the study for the subjects enrolled and to be enrolled. As a result, following each data review, the DMC will make a recommendation to the sponsor regarding continuation, revision, or termination of the study. Details related to DMC responsibilities, authorities, and procedures will be documented in the DMC charter, which will be finalized by the DMC prior to the first DMC data review meeting.

## 7. Changes in Planned Analysis

None

## 8. Data Issues

None

